### 3.2.3 ECD as Time Dependent Predictor of Graft Failure

The relationship between endothelial graft failure (graft failure due to endothelial decompensation) and ECD will be addressed paralleling the methods used in the CDS. A Cox model will be fit with ECD as a time dependant covariate. This analysis will be limited to subjects with at least one gradable follow up image. The rate of change will also be calculated as a time dependent variable defined as the least squares slope over all previous measurements starting at 6 months (e.g., the rate of change at one year would be the slope fit to the 6 month and 1 year ECD values). Missing values will be imputed by Rubin's method. If non-linear effects are detected, transformations will be used. For ease of interpretation, results will be presented as discrete categories with cutpoints chosen to display the trends identified from the transformed model. P-

460 values will still be from a continuous analysis although data are displayed as  
461 categories. The proportional hazards assumptions will be tested as described above.  
462

463 To check whether results are sensitive to how missing data are handled, a second  
464 model will be fit with a time dependent indicator for missing ECD.  
465

### 466 3.2.4 Secondary Outcome of Graft Rejection

467 Associations of baseline recipient and donor factors with the occurrence of a graft  
468 rejection will be assessed in univariate and multivariate proportional hazards models.  
469 Life-table analyses will be used to compute the probability of a first rejection event  
470 within intervals defined by the study exam schedule. Data will be censored at the time  
471 of a non-rejection graft failure or at the last visit.

472 A Kaplan-Meier approach will be considered for evaluating probability of first graft  
473 rejection, and time dependency of repeated rejection events will also be explored.  
474 Determination of the timing of a separate episode graft rejection will include a  
475 confirmation that the eye was off steroids at the visit where rejection was reported.  
476

## 477 4.0 Endothelial Cell Density (ECD)

### 478 4.1 Primary Analysis of 3 Year ECD- (Analysis plan for objective 2)

#### 479 4.1.1 Analysis Cohort

480 The primary analysis will include all study participants with a gradable 3-year image,  
481 who have not experienced graft failure 3 years after transplantation.  
482

#### 483 4.1.2 Outcome Measure

484 The primary outcome measure will be the ECD at 3 years, conditional on graft survival  
485 at 3 years.  
486

#### 487 4.1.3 Descriptive Statistics

- 488 489 • Summary statistics (mean  $\pm$  SD and/or median/quartiles as appropriate to the  
490 distribution) will be given for the ECD by the 2 treatment groups ( $\leq 7$  and 8 to 14  
491 days) and 4 treatment groups (0 – 4, 5 – 7, 8 – 11, and 12 – 14 days).
- 492 493 • Change from eye bank determined screening ECD will be summarized in a similar  
494 manner.
- 495 496 • Boxplots of ECD and change from eye bank determined screening ECD will be  
497 given for the 2 randomization groups.
- 498 499 • A scatter plot will be constructed of eye bank determined screening ECD vs. 3  
500 year ECD with a symbol used to denote the two randomization groups.

#### 501 4.1.4 Analysis

502 An ANOVA model with 3 year ECD as the dependent variable will be used to assess  
503 the effect of preservation time.

- 504 505 • Confounding with regard to screening ECD is not expected to be an issue due to  
506 anticipated balance via randomization. Therefore, an ANCOVA model adjusting  
507 for eye-bank-determined screening ECD will only be used if this measurement is  
508 considered good enough to expect to have any impact on reducing variance.
  - 509 510 ○ Although all screening images are being collected, CIARC is not grading  
511 them other than a general quality assessment. CIARC will grade a sample  
512 of screening images within each eye bank. If more than 75% of the graded

509 ECDs are within 10% of the eye bank determined ECDs, the eye bank  
510 determined ECDs will be included in the model.

511 • The time from preservation to surgery will be treated as a binary variable.  
512 • If residual values from the models above are highly skewed then a transformation  
513 (e.g., square root or logarithm) or non-parametric methods will be used instead.  
514 • Random effects will be modeled to account for any correlated data from the same  
515 donor and any correlated data from 2 study eyes of the same study participant.  
516 • Additional ANCOVA models will also adjust for other recipient/donor risk  
517 factors. Univariate models will be evaluated first, and factors from those models  
518 with a p value <0.10 will then be evaluated in a multivariate model. A final model  
519 will be constructed consisting of factors with a p value <0.01 following a  
520 backwards selection process  
521 • Random surgeon effects will also be explored using a mixed effects model.  
522 • Sensitivity analysis will also be performed to check whether results change  
523 meaningfully depending on how missing data are handled. The missing 3 year  
524 ECD values for subjects with surviving grafts at 3 years will be imputed and  
525 included in an analysis as described in the previous section. The data imputation  
526 will be performed by using Rubin's method of multiple imputation.

527

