# STATISTICAL METHODS

The approach to sample size and statistical analyses are summarized below. A detailed statistical analysis plan will be written and finalized prior to the completion of the study. The analysis plan synopsis in this chapter contains the framework of the anticipated final analysis plan.

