#### 1072 **7.2.4.4 Primary Analysis**

1073 The primary analysis will be limited to subjects with gradable 3 year images, who have not  
1074 experienced graft failure 3 years after transplantation. An ANCOVA model with 3 year ECD as  
1075 the dependent variable adjusting for eye-bank-determined screening ECD will be used to assess  
1076 the effect of preservation time. The time from preservation to surgery will be treated as a binary

1077 variable. If residual values from the models above are highly skewed then a transformation (e.g.,  
1078 square root or logarithm) or non-parametric methods will be used instead.

1079 • Random effects will be modeled to account for any correlated data from the same donor and  
1080 any correlated data from 2 study eyes of the same study participant.  
1081 • Additional ANCOVA models will also adjust for other recipient/donor risk factors, (if  $p <$   
1082 0.05. Random surgeon effects will also be explored using a mixed effects model.

1083

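### SAP 4.1.4 lets screening ECD into the main 3-year ECD model only if a reading-agreement check passes; adjusting always, as the protocol does, costs almost nothing and protects precision

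*Combined protocol and SAP*

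**What the plan says.** SAP 4.1.4, the main analysis for Objective 2, makes the unadjusted model the default: "An ANOVA model with 3 year ECD as the dependent variable will be used to assess" the effect of preservation time, as a binary variable, with random effects for donor and participant.

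The reason given is that "Confounding with regard to screening ECD is not expected to be an issue due to" balance expected from randomization. The SAP therefore uses ANCOVA with eye-bank screening ECD only if that reading is "considered good enough to expect to have any impact on reducing variance". To decide, CIARC grades a sample "of screening images within each eye bank. If more than 75% of the graded" "ECDs are within 10% of the eye bank determined ECDs, the eye bank" values go into the model. The number of images is not stated, nor whether the 75% is pooled or applied bank by bank.

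Protocol 7.2.4.4 has no such condition: the model has 3-year ECD as "the dependent variable adjusting for eye-bank-determined screening ECD will be used to assess" the preservation-time effect. The protocol's Chapter 7 says of itself that it "contains the framework of the anticipated final analysis plan". SAP 4.3, on pre-operative ECD, adjusts for the same eye-bank reading with no check.

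SAP 4.1.4 then adds: "Additional ANCOVA models will also adjust for other recipient/donor risk" factors, selected by p-value (below 0.10 to be considered, below 0.01 to stay).

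**The concern.** The condition and its purpose do not match. How far a covariate reduces residual variance depends on its correlation with the outcome among the eyes analysed. The check asks instead whether two readings of donor images agree in absolute terms. A constant proportional bias breaks agreement but hardly touches correlation, so the check can exclude a good covariate. It also has little to protect against, because a useless covariate costs one degree of freedom among more than a thousand.

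What is at stake is the width of the confidence interval for the main preservation-time effect on ECD. The same choice carries into the analyses that reuse this model: continuous and four-category preservation time (SAP 4.2.1), the imputation sensitivity analysis (SAP 4.1.4) and the 4- and 5-year endpoints (SAP 8.3).

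**Working it through.** **Inputs from the documents.** There is no sample-size or power calculation for ECD to reproduce. The number of eyes comes from the projection in SAP 8.1: 44 + 154 + 165 + 157 + 195 + 152 + 171 + 79 = 1117, and 1117/1330 = 84.0%, which matches the stated 84%. This is an upper bound for the ECD analysis, since ungradable images and failed grafts come off it. Protocol 3.1.1 requires an eye-bank ECD of at least 2300 cells/mm² for every donor, so the covariate should be available for essentially every eye.

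**Assumed, because the documents do not give them.** Correlation rho of screening with 3-year ECD, 0.1-0.5; SD of 3-year ECD, 500-700 cells/mm²; eyes treated as independent.

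**1. Cost of always adjusting if rho = 0.** Residual degrees of freedom go from 1117 - 2 = 1115 to 1114. The variance factor is 1 + 1/(n - 4) = 1 + 1/1113, or +0.09%, which is about +0.045% in the standard error (SE). Counting the lost degree of freedom in the residual mean square as well, sqrt[(1115/1114) × (1 + 1/1113)] - 1 = 0.09% in the SE, taken here as the upper bound. The break-even rho is 0.03 on the first count and 0.04 on the second.

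**2. Gain from adjusting.** The SE ratio is sqrt(1 - rho²). The 95% half-width is 1.96 × SD × sqrt(1 - rho²) × sqrt(4/1117); at rho = 0 it is 58.6 (SD 500) or 82.1 (SD 700) cells/mm².

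| rho | SE ratio | SE smaller by | Half-width smaller by (SD 500 / 700) |
|---|---|---|---|
| 0.1 | 0.995 | 0.5% | 0.3 / 0.4 |
| 0.2 | 0.980 | 2.0% | 1.2 / 1.7 |
| 0.3 | 0.954 | 4.6% | - |
| 0.4 | 0.917 | 8.3% | - |
| 0.5 | 0.866 | 13.4% | 7.9 / 11.0 |

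**3. What the check responds to.** Simulation with 1,000,000 draws per case: true ECD normal with mean 2700 and SD 250-350; eye-bank reading = true × (1 + bias) × (1 + noise); CIARC reading exact or with 3% noise; agreement means the two differ by no more than 10% of the eye-bank value. These parameters are assumptions. Each case was run with and without the 2300 cut.

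- Bias +10%, 3% noise: agreement 63% with CIARC exact, 59% with 3% noise in both readings. The check fails. Correlation with true ECD is 0.95-0.97, with or without the cut.
- No bias, 3% noise in both readings: about 98% agreement. The check passes.
- Bias +8%, 3% noise: 83% (passes) with CIARC exact; about 75%, just failing, with noise in both.
- No bias, 9% eye-bank noise, CIARC exact: 73.5% without the cut (fails), 77-78% with it (passes).
- Banks at -10%, 0 and +10% in equal shares, 3% noise, CIARC exact: 67% without the cut, about 70% with it; both fail. Correlation is 0.73-0.83 without the cut and 0.63-0.73 with it. Here the check rightly flags a weaker covariate. Yet if true ECD correlates 0.2-0.5 with the 3-year value, the reading still has rho from 0.2 × 0.63 = 0.126 to 0.5 × 0.73 = 0.365. The SE would be 1 - sqrt(1 - 0.126²) = 0.8% to 1 - sqrt(1 - 0.365²) = 6.9% smaller, against a cost below 0.1%.

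The +10% result is stable under every variant run. Those near 75% are not and serve only as illustration.

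**The case against.** The strongest defence is that nothing here is invalid. The check has numeric limits set in advance and uses neither 3-year ECD nor treatment group. An unadjusted comparison of randomized groups is sound, and the protocol's own description of Chapter 7 left the SAP free to refine it. All of that stands. A reader might infer that a data-dependent choice of model biases the estimate or inflates type I error, or that the SAP breaches the protocol; the documents support neither.

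The loss is also doubly conditional: the check must fail and the correlation must be material. With unbiased readings and modest noise it passes comfortably, and the SAP then fits the very covariate proposed here. This too stands. Nor is agreement irrelevant: random reading error and differing bank biases do weaken the covariate. The opposite error, letting in a useless covariate, costs under 0.1%.

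The additional models offset part of the loss. SAP 4.1.4 does not list their factors, but SAP 4.2.3 names screening ECD among the donor factors. Its t statistic would be about rho × sqrt[1115/(1 - rho²)]: 3.4 at rho 0.1 and 6.8 at rho 0.2, enough to survive selection. These remain data-selected models beside the main estimate, so the offset is partial. Donor random effects may also absorb some of what screening ECD explains for paired corneas, so the gains above may be overstated.

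Three further inferences go too far:

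- **Donor imbalance.** Recipient eyes are randomized, and the donor minimization in protocol 3.1.2 names only preservation-time subgroups, so a reader might suspect confounding by donor ECD. No imbalance is shown, both groups share the donor criteria, surgeons are masked to donor ECD, and SAP 6.0 tabulates donor characteristics by group.
- **Contradiction with SAP 4.1.3.** Change from screening ECD is summarized there without a check, but a descriptive summary and a model covariate serve different purposes.
- **An unworkable check.** The missing image count and pooling rule are gaps in detail, and pooled is the natural reading for a single inclusion decision. The count does matter near the limit: at a true agreement of 80%, the chance of passing is 63% with 20 images and 95% with 200.

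**Conclusion.** The point holds as a minor matter of efficiency in a secondary outcome. The agreement check is an imperfect proxy for the variance reduction it is meant to judge, and the protection it offers is worth at most about 0.09% of the SE at about 1,100 eyes. If it fails, the main estimate forgoes an SE reduction of about 0.5% at rho 0.1, 2% at rho 0.2 and 13% at rho 0.5.

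A reader might take the top of that range as the expected loss. The documents do not support this: they give no correlation, no SD and no probability of failing the check, and the calculation treats eyes as independent. At the lower end the loss is trivial. The case for change rests on the cost being lower still, and on the protocol and SAP 4.3 already using the covariate without condition.

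**What to change.** In SAP 4.1.4, make the main 3-year ECD model the ANCOVA with preservation-time group and eye-bank screening ECD always included, keeping the planned donor and participant random effects. This restores the protocol's model. Report the unadjusted ANOVA as supportive. Keep the 75%/10% comparison as a descriptive measure of reading quality, stating the number of images and whether it is pooled or per bank.

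Do not substitute the CIARC pre-operative ECD in this model. By protocol 3.1.3.2 and SAP 4.2.3 it is imaged after cutting or just before shipment, hence after some or all of the storage under study, so adjusting for it could remove part of the effect being estimated.

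The cost is a few lines of SAP text and one degree of freedom. No new data are needed.

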## 528 4.2 Secondary Analyses of 3 Year ECD

529

530

### 531 4.2.1 Preservation Time

532 The time from preservation to surgery is treated as a binary variable in the primary  
533 analysis of ECD (see above section). The analyses described above will be repeated  
534 with time from preservation to surgery treated as continuous (using time of day to  
535 calculate hours from preservation to surgery) or multi-category variable (0 – 4, 5 – 7,  
536 8 – 11, and 12 – 14 days from preservation to surgery) in separate models.

537

### 538 4.2.2 Longitudinal analysis

539 This analysis also will be limited to subjects with a surviving graft at 3 years. A  
540 repeated measures least squares regression model will be fit using all available images  
541 at baseline, 6 months, 1, 2, and 3 years. This analysis will be performed *with* and  
542 *without* imputation of missing data. Rubin's method of data imputation will be used  
543 to impute the ECD values for all missing time points. The time from preservation to  
544 surgery will be modeled as both continuous and categorical as described above. If  
545 residual values have a skewed distribution then transformation (e.g., square root or  
546 logarithm) or non-parametric analysis will be used.

547

### 548 4.2.3 Predictive factors – (*Analysis plan for objective 3, ECD outcome*)

549 This analysis also will be limited to subjects with a surviving graft at 3 years. The  
550 association of factors potentially related to 3 year ECD will be evaluated in  
551 univariate and multivariate ANCOVA models, adjusting for preservation time group  
552 regardless of statistical significance, and the reading center grading of pre-operative  
553 ECD (imaged post-cut if the eye bank was performing the cutting and imaged just  
554 prior to shipping if the surgeon was performing the cutting). This ECD value will be  
555 considered the baseline for these analyses. Univariate models will be evaluated  
first, and factors from those models with a p value <0.10 will then be evaluated in a

556 multivariate model. A final model will be constructed consisting of factors with a p  
557 value <0.01 following a backwards selection process.

558 Potential factors to evaluate include:

- 559 560 • Recipient factors
  - 561 ➤ preoperative diagnosis
  - 562 ➤ gender
  - 563 ➤ age
  - 564 ➤ race
  - 565 ➤ prior use of glaucoma medication
  - 566 ➤ prior glaucoma surgery (trabeculectomy, laser procedure)
  - 567 ➤ current smoker (at time of surgery)
  - 568 ➤ lens status (phakic, posterior chamber intraocular lens)
  - 569 ➤ Intraocular pressure (IOP)
- 570 571 • Donor/graft factors
  - 572 ➤ eye bank determined screening ECD
  - 573 ➤ pre-operative CIARC determined ECD
  - 574 ➤ age
  - 575 ➤ gender
  - 576 ➤ race
  - 577 ➤ history of diabetes
  - 578 ➤ cause of death
  - 579 ➤ type of storage medium
  - 580 ➤ death to preservation time
  - 581 ➤ surgeon cut vs eye bank cut
  - 582 ➤ postcut thickness
  - 583 ➤ cut to surgery time
  - 584 ➤ observations during or after cutting
- 585 586 • Surgical factors
  - 587 ➤ Insertion method
  - 588 ➤ Incision location
  - 589 ➤ Incision site
  - 590 ➤ Graft size
- 591 592 • Postoperative factors
  - 593 ➤ Dislocation
  - 594 ➤ Rebubbling
  - 595 ➤ IOP
  - 596 ➤ Graft rejection
  - 597 ➤ Corneal thickness

601 **4.3 Effect of Preservation Time on Pre-Operative ECD – (Secondary Non-Protocol  
602 Objective)**

603 An ANCOVA model with CIARC graded pre-operative ECD as the dependent variable,  
604 and adjusting for eye-bank-determined screening ECD, will be used to assess the effect

605 of preservation time. The time from preservation to surgery will be treated as a binary  
606 variable.  
607  
608

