#### 589 **3.1.3.2 Pre-Operative Images**

590 Three pre-operative images of the central donor corneal endothelium should be obtained in a  
591 viewing chamber by a certified technician, and submitted to the DMAC. If the eye bank is  
592 performing the cutting, the eye bank should obtain these pre-operative images after the tissue has  
593 been cut. If the surgeon is performing the cutting, the eye bank should obtain these pre-operative  
594 images as close as possible prior to shipment to the surgeon following appropriate warming to  
595 room temperature.

596

597  
598  
599  
600

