#### 1108 **7.2.5 Course of Cornea Changes After Endothelial Keratoplasty**

1109 The association of donor, operative and postoperative related factors with ECD will be evaluated  
1110 and assessed in univariate and multivariate ANCOVA models , adjusting for the reading center  
1111 grading of pre-operative ECD (imaged post-cut if the eye bank was performing the cutting and  
1112 imaged just prior to shipping if the surgeon was performing the cutting). This ECD value will be  
1113 considered the baseline for these analyses.

1114

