## 2.0 Sample Size

35 The sample size of 1330 is calculated based on a non-inferiority (a single one-sided test) design with  
36 the goal to determine that the graft failure rate of the recipients of donor tissue transplanted 8 to 14  
37 days after preservation is not worse than the graft failure rate of recipients of donor tissue transplanted  
38  $\leq$  7 days after preservation.

Non-Inferiority Limit	Power = 90 %				
	Failure Rate				
	12 %	10 %	8 % a	6 %	4 %
10 %	362	310			
8 %	566	482	394		
6 %	1006	858	702	538	
4 %	2262	1928	1576	1208	824
2 %	9044	7708	6304	4832	3290

40 Note: Numbers in table are total sample size for both treatment groups combined  
41 (crossover and lost to follow up are not accounted for). Half would be randomized to  
42 each group.

43 a CDS data: 3-year failure rate

45 In the Cornea Donor Study (CDS), the 3-year failure rate was 8%. Clinical expectations suggest that  
46 the graft failure rate from the EK procedure will be smaller than the failure rate from the PKP  
47 procedure that was used in CDS; therefore, a 3-year failure rate of 6% has been assumed. Based on  
48 equal allocation of recipients to each group and type I error of 5%, a sample size of 1208 will provide  
49 90% power for a non-inferiority limit of 4%. Based on information from the CDS, approximately  
50 10% of subjects will have incomplete follow up (due to death, withdrawal or lost to follow up) by the  
51 end of year 3. Increasing the calculated sample size by this amount gives a total of 1330 subjects  
52 (665 per group).

53 • The inclusion of participants with two study eyes, one in each treatment group, will tend to  
54 reduce the variance and as a result increase statistical power. To be conservative, this has not

55  
56  
57  
58  
59 been accounted for in the sample size estimation, since the correlation of outcome with two  
56 eyes is not known.  
57  
58

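### The Objective 3 ECD models adjust for a pre-operative ECD that includes the cutting loss only when the eye bank cut the tissue, so the comparison of surgeon-cut with eye-bank-cut tissue is biased if cutting costs cells

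*Combined protocol and SAP*

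**What the plan says.** SAP 4.2.3 puts the reading center's pre-operative ECD, together with preservation time group, into every univariate and multivariate model for 3-year ECD, and names it the baseline. It defines the value as "ECD (imaged post-cut if the eye bank was performing the cutting and imaged just" before shipping when the surgeon cuts. Protocol 7.2.5 has the same definition: "grading of pre-operative ECD (imaged post-cut if the eye bank was performing the cutting and" so on. Protocol 3.1.3.2 confirms the practice. Tissue cut by the eye bank is imaged after the cut. Otherwise, "If the surgeon is performing the cutting, the eye bank should obtain these pre-operative" images as late as possible before shipment, and so before the cut.

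The candidate factors in SAP 4.2.3 include which party cut the tissue and what was seen during or after cutting. Candidates with p<0.10 in the univariate models go forward, and backward selection keeps those with p<0.01. Cut type is not forced into the model.

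Two other sections bear on the point:

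- SAP 4.3 uses the same measurement as an outcome ("An ANCOVA model with CIARC graded pre-operative ECD as the dependent variable"), with preservation time as the factor.
- SAP 4.1.4, for Objective 2, uses an ANOVA without pre-operative ECD. Eye-bank screening ECD enters only if more than 75% of a reading-center-graded sample agrees with the eye bank within 10%.

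No section brings the two imaging times together, and none provides an Objective 3 ECD analysis without this covariate or within one cutting group.

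**The concern.** A baseline covariate should mean the same thing in the groups being compared. Here it is measured on opposite sides of the cut, and the cut is part of what is being compared. Suppose the surgeon and the eye bank lose the same number of cells in cutting. The eye-bank group then starts from a baseline that has already fallen, and the surgeon group from one that has not. The model sees surgeon-cut tissue reach the same 3-year ECD from a higher start and reports an adverse association with surgeon cutting.

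Cutting observations have a related problem. In eye-bank-cut tissue the model holds fixed an ECD that already reflects whatever the observation signals. In surgeon-cut tissue it does not. One coefficient then mixes two different quantities.

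At stake is a published statement, from a stated study objective, about who should cut the tissue. It could arise only from when the image was taken.

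**Working it through.** **1. The plan's own figure.** The only planning calculation in the documents is for the primary test (SAP 2.0: "equal allocation of recipients to each group and type I error of 5%, a sample size of 1208 will provide" the stated power). With a 6% failure rate, a 4% margin, one-sided 5% and 90% power, n per group = 2 × 0.06 × 0.94 × (1.645 + 1.282)² / 0.04² = 604, or 1208 in total. This matches. It does not bear on Objective 3, for which no precision or power is given.

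**2. What the baseline contains.** Let E be ECD just before the cut, Le the loss when the eye bank cuts and Ls the loss when the surgeon cuts.

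| | Eye-bank-cut | Surgeon-cut |
|---|---|---|
| Baseline in the model | E − Le | E |
| ECD entering the eye | E − Le | E − Ls |

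**3. Direction.** By the ANCOVA identity, adjusted contrast = unadjusted contrast − within-group slope × baseline difference. With equal E on average, the baseline difference (surgeon minus eye bank) is E − (E − Le) = Le. The adjustment therefore shifts the contrast by −slope × Le, whatever Ls is. If Ls = Le = L, the true contrast is 0 and the model reports about −slope × L. The shift vanishes only if cutting costs no cells or the slope is zero.

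**4. Size, on assumed inputs.** The documents give no cutting loss, slope or surgeon-cut share. Assumed values:

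- 1,000 eyes, 30% surgeon-cut
- pre-operative SD about 295 (√(280² + 80² + 50²))
- grading error SD 100
- residual SD of 3-year ECD 500
- equal cutting loss L in both groups

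Grading error reduces the slope by 87,300 / (87,300 + 10,000) = 0.897, so the expected contrast is −0.897 × slope × L. At L = 100 this gives −27, −54 and −90 for slopes 0.3, 0.6 and 1.0. A simulation of 200 data sets per setting, with a true contrast of 0, gave these contrasts in cells/mm². In brackets is the share of data sets with p<0.01.

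| L | slope 0.3 | slope 0.6 | slope 1.0 |
|---|---|---|---|
| 0 | −1 (1%) | 0 (3%) | −4 (1%) |
| 50 | −12 (2%) | −27 (4%) | −45 (8%) |
| 100 | −25 (3%) | −53 (13%) | −91 (50%) |
| 200 | −48 (9%) | −111 (67%) | −180 (98%) |

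With a common post-cut baseline, or with no baseline ECD, the contrast stayed within ±6.

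**5. Donor and storage factors.** Take a factor unrelated to cut type that lowers pre-operative ECD by an assumed 100 cells/mm² and acts only by that route. Its total effect on 3-year ECD is −30 to −100 for slopes of 0.3 to 1.0. At L = 100 the planned model shows −1 to −13. A model with no baseline ECD, or with screening ECD, returns −28 to −101. This is the expected result of asking a different question: the planned model describes loss after the image.

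**The case against.** **Donor and storage factors.** A reader might infer that the covariate biases the donor and storage factors generally. The documents do not support that. Unequal imaging time alone does not bias a factor unrelated to who cut. Adjusting for pre-operative ECD changes the quantity estimated, and protocol 7.2.5 is titled as the course of changes after the procedure, for which a pre-operative baseline is coherent. Objective 3 speaks of effects on 3-year ECD, which leans toward the total effect, so the target needs stating. That is a clarification and not an error.

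This defense does not rescue cut type. Even if the target is loss after the image, that loss includes the cut in one group and excludes it in the other.

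**Preservation time.** A reader might also infer that its effect on ECD is compromised. It is not. SAP 4.1.4 estimates it without pre-operative ECD, SAP 4.3 estimates the pre-operative part, and in SAP 4.2.3 preservation time is only an adjuster.

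**Size.** Every figure rests on assumed inputs, and with small losses or slopes the artifact seldom passes p<0.01. That stands. Cut type is one non-randomized factor among 31 listed, in a secondary screen.

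**Screening ECD as a substitute.** It is graded by the eye banks, and offsets between banks could track cut type. Assume a +100 offset in surgeon-cut tissue, a screening SD of 300 and an error SD of 150. The slope shrinks by 90,000 / 112,500 = 0.8, so the contrast is −0.8 × 0.5 × 100 = −40 at slope 0.5 and −80 at slope 1. This stands, and it is why screening ECD should be used only after the SAP 4.1.4 check, with no baseline ECD as the default.

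**Duplicate listing.** Pre-operative ECD is both forced in and listed as a candidate. This is editorial.

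**Conclusion.** The concern holds for cut type and cutting observations. The two imaging times are stated in the SAP and the protocol, and the direction of the bias follows from the model. The adjusted contrast is shifted against surgeon-cut tissue by about slope × cutting loss. Under assumed losses of 50 to 200 cells/mm² and slopes of 0.3 to 1.0 the shift is about −12 to −180 cells/mm², passing p<0.01 in 2% to 98% of simulated data sets. It is zero if cutting costs no cells. These sizes are illustrations, because the documents supply neither input.

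For donor and storage factors the finding is only that the target is unstated. The reach is limited to the secondary Objective 3 ECD models.

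**What to change.** In SAP 4.2.3, and in protocol 7.2.5 to match:

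1. Evaluate cut type and cutting observations without pre-operative ECD. Use no baseline ECD or, if it passes the SAP 4.1.4 agreement check, eye-bank screening ECD.
2. Where pre-operative ECD is kept as baseline for other factors, force in an indicator for pre- or post-cut imaging (equivalently, cut type) that is exempt from backward selection. State that its coefficient is not to be read as an effect of cutting.
3. For donor and storage factors, state that the model with pre-operative ECD estimates association with loss after the pre-operative image. Also report the model without that covariate, for the total association with 3-year ECD.

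As tidying, remove pre-operative ECD from the candidate list wherever it is already forced in.

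The cost is SAP wording and a few extra models. Both ECD measurements are already collected. The models without pre-operative ECD remove slightly less variance, and screening ECD, where used, brings the eye banks' own grading error.
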